2 OBJECTIVES

2.1 To achieve a prevalence of grade 3+ late toxicity at 2 yrs <15% while maintaining a locoregional tumor control >85±7% at the same time interval (toxicity is scored at 5.11 and 9.5 and locoregional control at 9.4);

2.2 To determine the nature and prevalence of side effects at different time intervals and describe their relationship to pretreatment function and local dose and treated volume.

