5.12 Toxicity Reporting Guidelines

5.12.1 For both acute and late effect, the NCI CTCAE Version 4.0 will be used (Appendix 1). All events will be recorded and loaded into software that is routinely used for clinical purposes in our Department called Mosaiq (v1.6 IMPAC, Sunnyvale, California).

5.12.2 The Head and Neck Cancer specific module of the MD Anderson Symptom Index (MDASI-HN)(Appendix 2) and the Xerostomia questionnaire (Appendix 3) will be used as patient-reported outcome instruments^{48,49}

5.12.3 The swallowing related instruments (see 1.6) are: Penetration/Aspiration scale (Appendix 4); Montreal Cognitive Assessment (Appendix 5); MD Anderson Dysphagia Inventory (MDADI)(Appendix 6).

5.12.4 All life-threatening (*grade 4*) toxicities from protocol treatment will be reported to the PI within 24 hours of discovery. **Institutional guidelines will be followed in reporting serious adverse events to the IRB.**

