10.3 Analysis of Endpoints

10.3.1. To achieve a prevalence of grade 3+ toxicities between six months and two years post-treatment <15% while maintaining a locoregional tumor control of at least 85% during the same time interval.

The primary endpoints, prevalence of toxicity and locoregional control rate, will be reported for all patients with an exact 95% confidence interval.

10.3.2. To determine the nature and prevalence of side effects at different time intervals and describe their relationship to pre-treatment function (toxicity) and local dose and treated volume.

Patients will be grouped by whether they had none or a grade 0-2 toxicity versus a grade 3+ toxicity. We will tabulate the frequency of patients in each group by a dichotomous measure of dose and tests for differences with a Chi-square or Fisher's exact test. Patients will also be grouped dichotomously by the number of side effects experienced

and frequencies will be compared to dose category and toxicity category using Chi-square or Fisher's exact tests.

10.3.3. To determine the quality of life of surviving patients.

The results of the Head and Neck MD Anderson Symptom Inventory (MDASI-HN) will be calculated for each patient. The mean score will be reported with a 95% confidence interval. The range and quartiles of the distribution of scores will also be reported.

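### Section 10.3.2 cuts the number of side effects into two groups at an unstated point, which discards power; analyse it as a count, and add an ordinal grade analysis beside the grade 3+ test

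*Combined protocol and SAP*

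**What the plan says.** Objective 2.2 is restated at the head of 10.3.2. It covers the nature and prevalence of side effects at different time intervals, and the aim to "describe their relationship to pre-treatment function (toxicity) and local dose and treated volume".

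Section 10.3.2 then reduces every variable to two levels:

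- **Grade:** "Patients will be grouped by whether they had none or a grade 0-2 toxicity versus a grade 3+ toxicity".
- **Dose:** "We will tabulate the frequency of patients in each group by a dichotomous measure of dose", followed by "tests for differences with a Chi-square or Fisher's exact test".
- **Number of side effects:** "Patients will also be grouped dichotomously by the number of side effects experienced", after which "frequencies will be compared to dose category and toxicity category using Chi-square or Fisher's exact tests".

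No cut-point is given for dose or for the number of side effects. No count, ordinal, trend or regression analysis is planned for this objective, and no power, alpha or effect size is stated for it.

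The underlying data are richer. Section 5.12.1 says: "For both acute and late effect, the NCI CTCAE Version 4.0 will be used (Appendix 1). All events will be recorded". Appendix 1 grades each item separately. Table 9 in section 9.1 schedules toxicity evaluation before treatment, weekly during radiotherapy and at follow-up. Section 9.5.1 defines severe toxicity as grade 3 or more and makes that the event.

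**The concern.** A patient with one side effect more than the cut is treated the same as a patient with many more, and two patients one apart can fall in different groups. In a trial of 50 to 60 patients, that loss can decide whether a real dose relationship is seen. Because the cut-point is not stated, it can also be chosen after the data are seen. No reason is given for cutting the count.

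The grade cut raises a related but weaker concern. It merges grades 0, 1 and 2, and at the 15% target rate it leaves few patients in the upper group. Unlike the count cut, it has a stated basis in 9.5.1.

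What is at stake is how informative objective 2.2 can be. The primary analysis is not involved.

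**Working it through.** **Inputs from the documents (section 10.1).** 60 enrolled, 50 evaluable, target maximum grade 3+ rate 15% between six months and two years.

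**Plan's own figures.** None is given for 10.3.2. The nearest ones reproduce: 7/50 has an exact 95% interval of 5.8-26.7%, half-width 10.5% (plan: 6-27%, 10.5%), and 60 × 0.85 = 51 (plan: 50).

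**Assumptions, because the documents give no figure.** Two-sided 5% tests; dose in two equal groups of 25; side-effect count with overall mean 4, 6 or 8, either Poisson or overdispersed (dispersion 0.2); rate ratio 1.5 between dose groups; count cut at the pooled median. With rate ratio 1.5 and overall mean m, the group means are 2m/2.5 = 0.8m and 1.2m, for example 3.2 and 4.8 when m = 4.

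**Count, simulated power at n = 50:**

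| Analysis | Power |
|---|---|
| Median cut, Fisher | about 32-85% |
| Median cut, Chi-square | about 43-92% |
| Wilcoxon on the count | about 50-97% |

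The low end of each row is the overdispersed case with mean 4, and the high end is the Poisson case with mean 8. Scenario by scenario, the uncut count gains about 13-24 points over Fisher and 6-12 over Chi-square. With no dose effect, rejection was 4.3-5.7% for Wilcoxon, 2.6-3.5% for Fisher on the median cut and 5.0-7.2% for Chi-square. An inflated error rate therefore does not explain the gain.

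A second model gives the same direction. It used a latent-normal correlation of 0.4 between dose and toxicity, dose split at its median and a Poisson count with mean 5. Power was about 36% for the cut count with Fisher and about 60% for the uncut count. In theory, a cut of a normal outcome at threshold t with upper fraction p keeps φ(t)²/[p(1−p)] of the information. At the median this is 0.159/0.25 = 0.64, and no other cut does better.

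**Grade.** At 15%, 50 × 0.15 = 7.5 patients are grade 3+, so an even dose split gives expected cells of 3.75. Three assumed distributions of grades 0-2 were used, under two patterns of dose effect:

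| Pattern of dose effect | Chi-square, 3+ vs 0-2 | Wilcoxon on grade |
|---|---|---|
| Whole scale shifts, odds ratio 3 (grade 3+ about 8% vs 22%) | about 26-27% | about 48-53% |
| Only grade 3+ changes (5% vs 25%) | about 54-56% | about 24-26% |

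The ranking reverses between the rows. The first pattern also depends on the event rate. At odds ratio 3 with 35% grade 3+, Chi-square has 45-46% and Wilcoxon 55%; at 50% the figures are 52% and 53%. Rates well above 15% are relevant because objective 2.2 also covers the acute period, and section 1.4 cites prevalences of 30.9%, 35.1% and 43% in earlier series.

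**The case against.** The strongest case for the plan is that objective 2.2 is secondary and descriptive, with no power claim or decision rule, and that the grade 3+ cut is pre-specified, clinically defined and the same event as the primary endpoint. For grade, this stands. Relating dose to the protocol's own severe-toxicity event is coherent, and the second pattern above shows that the 3+ test can be the more powerful one. A pooled worst grade also mixes items with different ceilings: in Appendix 1, dysgeusia stops at grade 2 and dry mouth at grade 3.

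For the count, the objection does not answer the point. No definition in the documents supports a two-way split, and 10.3.2 does specify hypothesis tests.

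It is also fair that dose itself is cut in two. That is a separate loss, and leaving the outcomes uncut will not recover it.

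Some stronger readings are tempting:

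- **That an ordinal grade test should replace the 3+ test.** This holds only if dose shifts the whole scale, which the documents do not establish. A worst late grade alone would also drop the time-interval part of objective 2.2.
- **That the planned tests would mostly find nothing.** The cut count still has 43-92% power with Chi-square in these scenarios.
- **That the case for de-escalation hangs on this analysis.** It rests on the radiobiology and dosimetry in section 1.5 and on the primary endpoint.
- **That the plan fixes an even dose split or a high/low count cut.** It states neither; the even split here is an assumption.

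**Conclusion.** The concern holds for the number of side effects. Cutting it in two at an unstated point loses about 13-24 points of power against Fisher and 6-12 against Chi-square at n = 50. This rests on the assumed mean count, dispersion, rate ratio 1.5, even dose split and median cut; the documents give none of these. The direction is the same in every scenario tried and in the second model.

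For grade, the conclusion is limited. The grade 3+ test is justified and should remain. An ordinal analysis would add information, but whether it gains or loses power depends on an unknown pattern of dose effect, so it belongs beside the 3+ test as support. The point concerns a secondary objective and leaves the primary endpoint untouched.

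**What to change.** In 10.3.2:

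1. Replace the two-way grouping of the number of side effects with an analysis of the count against dose and toxicity category, by Wilcoxon rank-sum or by Poisson or negative-binomial regression. This also removes the unstated cut-point for the count.
2. Keep the grade 0-2 versus 3+ test as planned, with a reference to 9.5.1.
3. Add, as a supporting analysis, worst CTCAE grade as an ordinal outcome (Wilcoxon or proportional odds) for each time interval, acute and late.
4. Leave 10.3.1 unchanged.

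The cost is a wording change, a few lines of code and one extra secondary analysis. No new data, visits or patients are needed. The downside is that a rank or rate-ratio result is less direct to state than a proportion.

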APPENDIX 1 CTCAE V4.0 TOXICITY

Grade	1	2	3	4	5

Gastrointestinal disorders: Mucositis oral
 
Definition: A disorder characterized by inflammation of the oral mucosal.
	Asymptomatic or mild symptoms; intervention not indicated	Moderate pain; not interfering with oral intake; modified diet indicated	Severe pain; interfering with oral intake	Life-threatening consequences; urgent intervention indicated	Death

Injury, poisoning, & procedural complications: Skin Radiation recall reaction (dermatologic)
 
Definition: A finding of acute skin inflammatory reaction caused by drugs, especially chemotherapeutic agents, for weeks or months following radiotherapy. The inflammatory reaction is confined to the previously irradiated skin and the symptoms disappear after the removal of the pharmaceutical agent.
 
OR
 
Injury, poisoning, & procedural complications: Dermatitis radiation (Definition: A finding of cutaneous inflammatory reaction occurring as a result of exposure to biologically effective levels of ionizing radiation).
	Faint erythema or dry desquamation	Moderate to brisk erythema; patchy moist desquamation, mostly confined to skin folds and creases; moderate edema	Moist desquamation in areas other than skin folds and creases; bleeding induced by minor trauma or abrasion	Life-threatening consequences; skin necrosis or ulceration of full thickness dermis; spontaneous bleeding from involved site; skin graft indicated	Death

Grade	1	2	3	4	5
Musculoskeletal & connective tissue disorders: Superficial soft tissue fibrosis Definition: A disorder characterized by fibrotic degeneration of the superficial soft tissues.	Mild induration, able to move skin parallel to plane (sliding) and perpendicular to skin (pinching up)	Moderate induration, able to slide skin, unable to pinch skin; limiting instrumental ADL	Severe induration; unable to slide or pinch skin; limiting joint or orifice movement (e.g. mouth, anus); limiting self care ADL	Generalized; associated with signs or symptoms of impaired breathing or feeding	Death
Gastrointestinal disorders: Dry mouth Definition: A disorder characterized by reduced salivary flow in the oral cavity.	Symptomatic (e.g., dry or thick (saliva) without significant dietary alteration; unstimulated saliva flow >0.2 ml/min	Moderate symptoms; oral intake alterations (e.g., copious water, other lubricants, diet limited to purees and/or soft, moist foods); unstimulated saliva 0.1 to 0.2 ml/min	Inability to adequately aliment orally; tube feeding or TPN indicated; unstimulated saliva <0.1 ml/min		
Nervous system disorders: Dysgeusia Definition: A disorder characterized by abnormal sensual experience with the taste of foodstuffs; it can be related to a decrease in the sense of smell.	Altered taste but no change in diet	Altered taste with change in diet (e.g., oral supplements); noxious or unpleasant taste; loss of taste			
Gastrointestinal disorders: Nausea Definition: A disorder characterized by a queasy sensation and/or the urge to vomit.	Loss of appetite without alteration in eating habits	Oral intake decreased without significant weight loss, dehydration or malnutrition	Inadequate oral caloric or fluid intake; tube feeding, TPN, or hospitalization indicated		Death
Gastrointestinal disorders: Vomiting Definition: A disorder characterized by the	1 – 2 episodes (separated by 5 minutes) in 24 hrs	3 – 5 episodes (separated by 5 minutes) in 24 hrs	>=6 episodes (separated by 5 minutes) in 24 hrs; tube feeding, TPN or	Life-threatening consequences; urgent intervention indicated	Death

reflexive act of ejecting the contents of the stomach through the mouth.			hospitalization indicated		
Metabolism & nutrition disorders: Dehydration Definition: A disorder characterized by excessive loss of water from the body. It is usually caused by severe diarrhea, vomiting or diaphoresis.	Increased oral fluids indicated; dry mucous membranes; diminished skin turgor	IV fluids indicated <24 hrs	IV fluids or hospitalization indicated	Life-threatening consequences; urgent intervention indicated	Death
Gastrointestinal disorders: Dysphagia Definition: A disorder characterized by difficulty in swallowing.	symptomatic, able to eat regular diet	Symptomatic and altered eating/swallowing	Severely altered eating/swallowing; tube feeding or TPN or hospitalization indicated	Life-threatening consequences; urgent intervention indicated	Death
Respiratory, thoracic, & mediastinal disorders: Aspiration Definition: A disorder characterized by inhalation of solids or liquids into the lungs.	Asymptomatic; clinical or diagnostic observations only; intervention not indicated	Altered eating habits; coughing or choking episodes after eating or swallowing; medical intervention indicated (e.g., suction or oxygen))	Dyspnea and pneumonia symptoms (e.g., aspiration pneumonia); hospitalization indicated; unable to aliment orally	Life-threatening respiratory or hemodynamic compromise; intubation or urgent intervention indicated	Death
Respiratory, thoracic, & mediastinal disorders: Cough Definition: A disorder characterized by sudden, often repetitive, spasmodic contraction of the thoracic cavity, resulting in violent release of air from the lungs and usually accompanied by a distinctive sound.	Mild symptoms; nonprescription intervention indicated	Moderate symptoms, medical intervention indicated; limiting instrumental ADL	Severe symptoms; limiting self care ADL		

Gastrointestinal disorders: Esophageal stenosis
 
Definition: A disorder characterized by a narrowing of the lumen of the esophagus.
	
Asymptomatic; clinical or diagnostic observations only; intervention not indicated
	
Symptomatic; altered GI function
	
Severely altered GI function; tube feeding; hospitalization indicated; elective operative intervention indicated
	
Life-threatening consequences; urgent operative intervention indicated
	
Death

Investigations: Weight loss
 
Definition: A finding characterized by a decrease in overall body weight; for pediatrics, less than the baseline growth curve.
	
5 to <10% from baseline; intervention not indicated
	
10 - <20% from baseline; nutritional support indicated
	
>=20% from baseline; tube feeding or TPN indicated
		

Infections & infestations: Wound infection
 
Definition: A disorder characterized by an infectious process involving the wound.
		
Localized; local intervention indicated (e.g., topical antibiotic, antifungal, or antiviral)
	
IV antibiotic, antifungal, or antiviral intervention indicated; radiologic or operative intervention indicated
	
Life-threatening consequences; urgent intervention indicated
	
Death


Blood & lymphatic system disorders: Febrile neutropenia
 
Definition: A disorder characterized by a decrease in neutrophils associated with fever.
			
present
	
Life-threatening consequences; urgent intervention indicated
	
Death

Blood & lymphatic system disorders: Anemia
 
Definition: A disorder characterized by an reduction in the amount of hemoglobin in 100 ml of blood. Signs and symptoms of anemia may include pallor of the skin and mucous membranes, shortness of breath, palpitations of the heart, soft systolic
	
Hemoglobin (Hgb) <LLN – 10.0 g/dL; <LLN – 6.2 mmol/L; <LLN – 100 g/L
	
Hgb <10.0 – 8.0 g/dL; <6.2 – 4.9 mmol/L; <100 – 80g/L
	
Hgb <8.0 – 6.5 g/dL; <4.9 – 4.0 mmol/L; <80 – 65 g/L; transfusion indicated
	
Life-threatening consequences; urgent intervention indicated
	
Death

murmurs, lethargy, and fatigability.					
--------------------------------------	--	--	--	--	--

Investigations: White blood cell decreased
 
Definition: A finding based on laboratory test results that indicate an decrease in number of white blood cells in a blood specimen.
	<LLN – 3000/mm ³ ; <LLN – 3.0 x 10 ⁹ /L	<3000 – 2000/mm ³ ; <3.0 – 2.0 x 10 ⁹ /L	<2000 – 1000/mm ³ ; <2.0 – 1.0 x 10 ⁹ /L	<1000/mm ³ ; <1.0 x 10 ⁹ /L	Death

Investigations: Neutrophil count decreased
 
Definition: A finding based on laboratory test results that indicate a decrease in number of neutrophils in a blood specimen.
	<LLN – 1500/mm ³ ; <LLN – 1.5 x 10 ⁹ /L	<1500 – 1000/mm ³ ; <1.5 – 1.0 x 10 ⁹ /L	<1000 – 500/mm ³ ; <1.0 – 0.5 x 10 ⁹ /L	<500/mm ³ ; <0.5 x 10 ⁹ /L	Death

Investigations: Platelet count decreased
 
Definition: A finding based on laboratory test results that indicate a decrease in number of platelets in a blood specimen.
	<LLN - 75,000/mm ³ ; <LLN - 75.0 x 10 ⁹ /L	<75,000 - 50,000/mm ³ ; <75.0 - 50.0 x 10 ⁹ /L	<50,000 - 25,000/mm ³ ; <50.0 - 25.0 x 10 ⁹ /L	<25,000/mm ³ ; <25.0 x 10 ⁹ /L	Death

Respiratory, thoracic, & mediastinal disorders: Voice alteration
 
Definition: A disorder characterized by a change in the sound and/or speed of the voice.
	Mild or intermittent change from normal voice	Moderate or persistent change from normal voice; still understandable	Severe voice changes including redominantly whispered speech; may require frequent repetition or face-to-face contact for understandability; may require assistive technology		Death

Respiratory, thoracic, & mediastinal disorders: Laryngeal edema
	Asymptomatic; clinical or diagnostic observations only;	Symptomatic; medical intervention indicated (e.g., dexamethasone,	Stridor; respiratory distress; hospitalization indicated	Life-threatening airway compromise; urgent intervention	Death

Definition: A disorder characterized by swelling due to an excessive accumulation of fluid in the larynx.	intervention not indicated	epinephrine, antihistamines)		indicated (e.g., tracheotomy or intubation)	
Musculoskeletal & connective tissue disorders: Osteonecrosis of jaw Definition: A disorder characterized by a necrotic process occurring in the bone of the mandible.	Asymptomatic; clinical or diagnostic observations only; intervention not indicated	Symptomatic; medical intervention indicated (e.g., topical agents); limiting instrumental ADL	Severe symptoms; limiting self care ADL; elective operative intervention indicated	Life-threatening consequences; urgent intervention indicated	Death
Gastrointestinal disorders: Dental caries	One or more dental caries, not involving the root	Dental caries involving the root	Dental caries resulting in pulpitis or periapical abscess or resulting in tooth loss		
Musculoskeletal & connective tissue disorders: Trismus Definition: A disorder characterized by lack of ability to open the mouth fully due to a decrease in the range of motion of the muscles of mastication.	Decreased ROM (range of motion) without impaired eating	Decreased ROM requiring small bites, soft foods or purees	Decreased ROM with inability to adequately aliment or hydrate orally		
Nervous system disorders: Myelitis Definition: A disorder characterized by inflammation involving the spinal cord. Symptoms include weakness, paresthesia, sensory loss, marked discomfort and incontinence.	Asymptomatic; mild signs (e.g., Babinski's reflex or Lhermitte's sign)	Moderate weakness or sensory loss; limiting instrumental ADL	Severe weakness or sensory loss; limiting self care ADL	Life-threatening consequences; urgent intervention indicated	Death
Nervous system disorders: Neuralgia	Mild pain	Moderate pain; limiting instrumental	Severe pain; limiting self care ADL		

Definition: A disorder characterized by intense painful sensation along a nerve or group of nerves.
		ADL			

General disorders & administration site conditions: Fatigue
 
Definition: A disorder characterized by a state of generalized weakness with a pronounced inability to summon sufficient energy to accomplish daily activities.
	Fatigue relieved by rest	Fatigue not relieved by rest; limiting instrumental ADL	Fatigue not relieved by rest, limiting self care ADL		

Ear & labyrinth disorders: Hearing impaired
 
Definition: A disorder characterized by partial or complete loss of the ability to detect or understand sounds resulting from damage to ear structures.
	
Adults enrolled on a monitoring program (a 1, 2, 3, 4, 6 and 8 kHz audiogram): threshold shift of 15 – 25 dB averaged at 2 contiguous test frequencies in at least one ear or subjective change in the absence of a Grade 1 threshold shift
	
Adults enrolled in monitoring program (a 1, 2, 3, 4, 6 and 8 kHz audiogram): threshold shift of >25 dB averaged at 2 contiguous test frequencies in at least one ear. Adult not enrolled in monitoring program: hearing loss but hearing aid or intervention not indicated; limiting instrumental ADL
	
Adults enrolled in monitoring program (a 1, 2, 3, 4, 6 and 8 kHz audiogram): threshold shift of >25 dB averaged at 3 contiguous test frequencies in at least one ear; therapeutic intervention indicated. Adults not enrolled in monitoring program: hearing loss with hearing aid or intervention indicated;
	Adults: profound bilateral hearing loss (>80 dB at 2 kHz and above); non-serviceable hearing	

Ear & labyrinth disorders: Tinnitus
 
Definition: A disorder characterized by noise in the ears, such as ringing, buzzing, roaring or clicking.
	Mild symptoms; intervention not indicated	Moderate symptoms; limiting instrumental ADL	Severe symptoms; limiting self care ADL		

Neoplasms benign, malignant, & unspecified: Treatment related secondary Malignancy Definition: A disorder characterized by development of a malignancy most probably as a result of treatment for a previously existing malignancy.			Non life-threatening secondary malignancy	Acute life-threatening secondary malignancy; blast crisis in leukemia	Death
Ear & labyrinth disorders: Vertigo Definition: A disorder characterized by a sensation as if the external world were revolving around the patient (objective vertigo) or as if he himself were revolving in space (subjective vertigo).	Mild symptoms	Moderate symptoms; limiting instrumental ADL	Severe symptoms; limiting self care ADL		
Performance status (ECOG)	1	2	3	4	5
PEG tube	No	Yes			
PO	No	Yes			
Admission(s)	No	Yes	# days _____		
Weight (kg)					

Items in grey denote modifications and additions to the original scale

